8.2.4.2. Summarization of ADA and nAb Results

1. The number of samples analyzed for ADA and nAb will be summarized.
2. ADA and nAb results will be summarized as categorical endpoints by visit and overall incidence at the subject level. The numbers and percentages of ADA positive and nAb positive subjects will be classified according to (1) timing of result with respect to bococizumab dosing (on treatment/off treatment), (2) characterization of ADA and nAb response (treatment induced/treatment boosted/indeterminate), and (3) duration of ADA and nAb response (indeterminate/persistent/transient) using the definitions in [Section 8.2.4.1.1](#) will be presented. The summary of nAb status will be performed with two different denominators: number of subjects with non-missing ADA samples and number of ADA positive subjects.
3. ADA titers for ADA positive subjects and nAb titers for nAb positive subjects will be summarized by visit as continuous endpoints. Boxplots of ADA titer and nAb titer over time will be presented for ADA positive subjects and nAb positive subjects, respectively.
4. Time to first positive ADA result and time to first positive nAb result will be summarized as continuous endpoints in subjects who are ADA positive or nAb positive, respectively.

A listing will also be provided that details subject identifier, treatment group, ADA titer, ADA status, nAb titer, nAb status, ADA induction type, nAb induction type, duration of ADA response, duration of nAb response, relative days to first positive ADA detection, relative days to first positive nAb detection, and day on study.

8.2.4.3. Summarization of Pharmacokinetics/Pharmacodynamics Results

The following analyses will be performed for plasma bococizumab concentrations, and LDL-C response. The windows from [Table 3](#) in [Appendix 1.1](#) will be used.

1. Listings of all plasma bococizumab concentrations by subject and visit will be provided.
2. Descriptive summaries of observed plasma bococizumab concentrations over time will be provided. Summary statistics will include arithmetic mean, standard deviation, % coefficient of variation, median, minimum, and maximum. The number of concentrations above the lower limit of quantification (NALQ) may also be provided. Observations below the lower limit of quantification will be imputed as zero.
3. Mean (\pm SD) observed bococizumab concentration will be plotted over time.

The following summaries will be provided using only observations meeting the following conditions (without missed doses and prior to dose adjustment):

- Sample collection date minus the previous injection date is between 1 and 21 days.
 - No dose adjustments have occurred prior to sample collection.
1. For plasma bococizumab concentrations, the descriptive summaries, longitudinal mean (\pm SD) plots will be repeated.
 2. For plasma bococizumab concentrations and LDL-C, the descriptive summaries will be repeated by ADA status and by nAb status. For plasma bococizumab concentrations only, box plots by ADA status and nAb status will be presented. For LDL-C, box plots of percent change from baseline will be repeated by ADA status and by nAb status.
 3. For plasma bococizumab concentrations and LDL-C, the descriptive summaries will be repeated by duration of ADA response (indeterminate/persistent/transient) and by duration of nAb response (indeterminate/persistent/transient). For LDL-C, and box plots of percent change from baseline will be repeated by duration of ADA response (indeterminate/persistent/transient) and by duration of nAb response (indeterminate/persistent/transient).

4. For plasma bococizumab concentrations and LDL-C, the descriptive summaries will be repeated by pre-existing ADA status (with pre-existing ADAs, without pre-existing ADAs).
5. For plasma bococizumab concentrations and LDL-C, the descriptive summaries will be repeated by ADA (nAb) titer response (ADA (nAb) negative, ADA (nAb) 1st tertile, ADA (nAb) 2nd tertile, ADA (nAb) 3rd tertile).

A comprehensive listing of plasma bococizumab concentration, LDL-C, ADA status, ADA titer, nAb status, and nAb titer will be provided by subject and visit for ADA positive subjects.

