**Lipid, ADA, PK, and PCSK9 testing requirements after randomization:**

Lipid (direct LDL-C and lipid panel), ADA, PK, and PCSK9 testing, after randomization, when required, should be scheduled **no sooner than 10 days after the subject's prior dose**, even if this requires an unscheduled visit. If a subject has a visit that is scheduled less than 10 days after the last dose, the visit procedures may take place, but lipid, ADA, PK, and PCSK9 testing should be postponed and performed at the earliest possible time, at an unscheduled visit, no sooner than 10 days after the subject's last dose. A lipid profile will not be collected at EDC/EOS visits. ADA, PK, and PCSK9 samples will be collected at EDC/EOS visits.

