**Dosing windows:**

After randomization, IP dosing windows are 1 day before or up to 4 days after the scheduled dosing date. If more than 4 days after the scheduled day have passed, the subject should skip the dose and resume dosing following the dosing schedule provided by site personnel for the next injection.

**Visit 2**, start of run-in: Run-in Visit 2 can occur up to 14 days after Visit 1, depending upon the availability of Visit 1 lab results, additional medical records, if they are needed, and the schedule of the subject and clinical site. At Run-in Visit 2, the initiation of the run-in period, the subject will be shown how to self-inject IP (placebo). Only during the run-in period (Visits 2, 3, and 4), subjects will be seen up to two weeks apart (0.5 month periods), to ascertain the subjects' ability to self-inject IP. The other run-in procedures specified in this [Schedule of Activities](#) will be adhered to.

**Visit sequences:** After Visit 5 (Week 0) subjects will be seen at Visit 6 (Week 4), Visit 7 (Week 8), Visit 8 (Week 14), Visit 9 (Week 26), Visit 10 (Week 40), and Visit 11 (Week 52). After Visit 11, subjects will be seen as indicated in the [Schedule of Activities](#). Subjects who discontinue IP early (EDC), will be encouraged to be followed, according to the visit schedule and activities, until study completion (EOS). If the study is not completed by Visit 20, visits will continue every 4 months in accordance with the [Schedule of Activities](#) for annual (Visits 11, 14, 17, 20) and interim visits (eg, Visits 12, 13, 15, 16, 18, and 19) until study completion (EOS). The study may end sooner than Visit 20, if the primary endpoint event accrual rate is faster than anticipated or the trial is terminated for other reasons. Subjects who have had an IP dose frequency modification to dosing every 4 weeks, will need to have their visit frequency increased to every 8 weeks, approximately, for the purposes of direct LDL-C measurement and an assessment for adverse events; both serious and non-serious ([Section 6.4.5](#)). If the per-protocol scheduled visit falls within the 8 week window, the scheduled visit will reset the scheduling of the next 8 week direct LDL-C measurement visits.

- 2 **IRT.** The subjects' visits will be registered at Visit 0 and every visit thereafter, unless they have discontinued treatment with IP.

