**Table 1. Treatments**

Group	
I	bococizumab, 150 mg SC, Q2wks
II	Placebo injection, SC, Q2wks

The IRT system will be used for each study visit, during the active treatment period, to assign IP for each subject. For subjects who are randomized to the active treatment arm, blinded bococizumab will initially be administered at a dose of 150 mg SC Q2wks. For subjects who are randomized to placebo, blinded placebo will initially be administered SC Q2wks. Blinded dose modifications may take place, through the IRT system, based on trigger measurements of LDL-C (5.4.1.1).

At Visit 5, after the subject has been randomized, and all other procedures and assessments completed, the first active treatment period dose will be self-injected, or injected by a care-giver, at the clinic. The subject will be observed at the study site, by the study site personnel, for 30 minutes after the self-injection. Subjects will be provided with a dosing schedule by site personnel based on the date of randomization. Subjects will receive sufficient pre-filled syringes (PFSs) to self-inject between clinic visits. As noted in the [Schedule of Activities](#), many of the scheduled doses will also coincide with scheduled visits. When a scheduled dose occurs on the same day as a scheduled visit, subjects should hold their self-injected dose until they are at the clinic and self-inject or be administered an injection by a care provider only after all other study procedures for that visit have been completed.

Injections 1 day before or up to 4 days past the scheduled day of administration are allowed. If more than 4 days after the scheduled day have passed, the subject should skip the dose and resume dosing following the dosing schedule provided by site personnel for the next injection.

Subjects should adhere to their treatment schedule even if their scheduled clinic visit is rescheduled or missed due to unforeseen circumstances.

Subjects will continue to receive their prescribed, background lipid lowering therapy, at the dose that they had taken at the last visit of the run-in period prior to the randomization visit.

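### The 1–21 day sample filter in SAP 8.2.4.3 does not guarantee freedom from missed doses, and does not restrict the antibody-group PK and LDL-C summaries to end-of-interval samples

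*SAP*

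**What the plan says.** SAP 8.2.4.3 first summarizes all bococizumab concentrations. It then plans a second set of concentration and LDL-C summaries "using only observations meeting the following conditions (without missed doses and prior to dose adjustment". Two conditions follow. One excludes samples taken after any dose adjustment. The other is "Sample collection date minus the previous injection date is between 1 and 21 days". This second set is the one split by ADA and nAb status, duration of response, pre-existing ADA, and titer tertile.

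The protocol's rules on dosing and sampling are these:

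- The starting regimen (Table 1) is "bococizumab, 150 mg SC, Q2wks".
- Schedule of Activities, Dosing windows: "After randomization, IP dosing windows are 1 day before or up to 4 days after the scheduled dosing date". The same paragraph adds: "If more than 4 days after the scheduled day have passed, the subject should skip the dose".
- Schedule of Activities, testing requirements after randomization: lipid, ADA and PK samples are to be scheduled "no sooner than 10 days after the subject's prior dose". If a visit comes earlier, "lipid, ADA, PK, and PCSK9 testing should be postponed and performed at the earliest possible time, at an unscheduled visit".
- Section 7.4.1: PK samples are drawn before that day's dose.
- Section 7.2.7.2: ADA and PK samples are also drawn at any hypersensitivity reaction, and when an injection site reaction persists past the third day after dosing. No 10-day floor is stated for these.
- Section 8.4 (Medication Errors): a single out-of-window dose is not an error if at least 7 days separate it from its neighbours.

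**The concern.** The description attached to these summaries is a claim about dosing history: no dose missed. The filter tests only the time from the latest injection to the sample. That cannot establish the claim, and both limits are wider than the protocol's own rules.

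What is at stake is the reading of the antibody comparisons. Concentration and LDL-C depend on time since dose. If the groups differ in sample timing or in earlier missed doses, a difference between them may partly reflect timing or adherence, or a real loss of exposure may be hidden. The reaction-triggered samples matter most here, because their triggers may themselves be related to antibodies.

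**Working it through.** **Inputs.** Dosing interval 14 days (Protocol Table 1). Dosing window −1 to +4 days (Dosing windows). Sampling floor 10 days (testing requirements). SAP filter 1 to 21 days (8.2.4.3).

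**Gap between two in-window doses.** Let the previous dose be *a* days and the next dose *b* days from schedule, each between −1 and +4. Then gap = (14 + *b*) − *a*.

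- Shortest: *a* = +4, *b* = −1, so 14 − 1 − 4 = 9 days.
- Longest: *a* = −1, *b* = +4, so 14 + 4 + 1 = 19 days.

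With the 10-day floor, a scheduled pre-dose sample with no skipped dose falls at 10 to 19 days. Day 19 is reached only if the previous dose was a day early. With that dose on schedule the limit is 14 + 4 = 18.

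**Comparison with the SAP filter.**

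| Days since injection | Day values accepted | Relation to protocol rules |
|---|---|---|
| 1–9 | 9 | before the scheduled-sampling floor |
| 10–19 | 10 | compatible |
| 20–21 | 2 | beyond the longest in-window gap |

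**Can 1 or 21 be derived?** Not from the dosing and sampling windows. Section 8.4 gives one possible route to the upper limit: with neighbouring doses on schedule 28 days apart and 7 days' separation from the next, the latest late dose is at 28 − 7 = 21 days. The SAP does not cite this rule. No rule yields the lower limit of 1.

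**Can the filter see a skipped dose?** Take doses due on days 0, 14 and 28, with day 14 skipped.

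- Sample on day 28 before dosing: gap 28, excluded.
- Dose taken on day 28, sample on day 42: gap 42 − 28 = 14, accepted. The skipped dose is not seen.

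The second result is the same under a 10–19 day filter, so narrowing the limits alone is not enough.

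**Reaction-triggered samples.** Protocol 7.2.7.2 asks for ADA, PK and PCSK9 but no lipid sample, so this route affects the concentration summaries and not LDL-C. When several measurements share an analysis window, SAP Appendix 1.1 keeps the one nearest the target day. That limits how many triggered samples enter, but it does not select on time since dose.

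**Does timing matter?** Protocol 1.2.5 gives Phase 2b LDL-C differences for 4-weekly dosing: −27.8 to −45.2 mg/dL at trough, and −46.8 to −55.5 mg/dL for the mean of nadir and trough. If the range endpoints belong to the same doses (an assumption), the shifts are −46.8 − (−27.8) = −19.0 and −55.5 − (−45.2) = −10.3 mg/dL. These are other regimens, so they show only that timing can matter.

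**The case against.** The strongest reply is that timing is already controlled when samples are collected. If sites follow the 10-day rule and draw PK before dosing, scheduled samples fall near the end of the interval whatever lower limit the SAP uses. The summaries are descriptive. Unfiltered concentration summaries and full listings are also planned, and the secondary LDL-C analyses do not use this filter. All of this stands and keeps the point minor. It does not make the description true, because collection rules do not reveal an earlier skipped dose and do not cover the reaction-triggered samples.

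A reader might infer four stronger things that the documents do not support.

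- *That the protocol forbids samples before day 10.* The rule concerns scheduling and postponement, and section 7.2.7.2 directs some ADA and PK samples that may fall earlier.
- *That the comparison is not made at trough.* The SAP never promises a trough analysis, and most scheduled samples should fall at 10–19 days if the protocol is followed. It can only be said that the comparison is not restricted to such samples.
- *That samples on days 20–21 follow a missed dose.* They show that the due dose was not taken within its window. Under the skip rule it should have been omitted; under section 8.4 it could still come late.
- *That the timing shift is as large as an antibody effect.* The documents give no antibody effect in mg/dL. They report only a potential PK or PD impact in 5 of 398 subjects (Protocol 1.2.3).

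**Conclusion.** The point holds in a limited form. The filter accepts 1–21 days where the protocol's rules imply 10–19, and it checks only the latest gap. It can also admit reaction-triggered PK samples from before day 10, which may not be balanced by ADA status. The condition the SAP states is therefore not guaranteed, and the summaries by ADA, nAb and titer group are not restricted to end-of-interval samples.

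The 10–19 day range assumes 2-weekly dosing before any adjustment, doses within the stated window, and samples drawn before that day's dose. The number of affected samples, and the direction and size of any bias, cannot be computed: the documents give neither sample-timing data nor a concentration profile for this regimen. Bias between antibody groups requires that timing or missed doses differ between them, which is possible but not shown. No test, alpha level or power figure is involved, and the primary and key secondary analyses are unaffected.

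**What to change.** In SAP 8.2.4.3:

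1. Restrict the filtered summaries to samples 10–19 days after the previous injection, or justify 1–21.
2. Use the dosing records to confirm that the scheduled dose before that injection was also taken, and state how far back the check reaches. SAP 6.3 says the date and time of each dose are already collected.
3. Exclude or flag samples drawn because of a reaction under Protocol 7.2.7.2.
4. Keep the 1–21 day version as a sensitivity summary.

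The skip rule under Dosing windows and the out-of-window rule in Protocol 8.4 should be reconciled, so that late and missed doses are defined consistently for this filter. This review takes no position on which rule should prevail.

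The cost is a few lines of SAP text, a revised filter and one extra set of descriptive tables. Some samples drop out of the main filtered summaries; how many is not known. If none of this is done, the description as free of missed doses should be removed.

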8.2.4.4. Adverse Events, Serious Adverse Events, and Deaths

Adverse events and serious adverse events will be summarized by ADA status (positive, negative) and by nAb status (positive, negative).

8.2.4.5. Injection Site Adverse Events

Injection site adverse events will be summarized by ADA status (positive, negative) and by nAb status (positive, negative). The higher level term of “injection site reactions” will be used to identify the adverse events.

8.2.4.6. Clinical Laboratory Measurements

Liver function test elevations will be summarized by ADA status and by nAb status. Additionally, the maximum post-randomization total bilirubin value will be plotted against the maximum post-randomization alanine transaminase (ALT) value by ADA status (positive, negative) and by nAb status (positive, negative).

Incidence of creatinine elevations will be summarized by ADA status (positive, negative) without regard to baseline abnormality, with normal baseline, and with abnormal baseline.

8.2.4.7. Outcomes Research Endpoints

EQ-5D

As a result of the discontinuation of the bococizumab clinical development program, EQ-5D will not be summarized as described in the protocol or listed.

Health Care Resource Utilization

As a result of the discontinuation of the bococizumab clinical development program, health care resource utilization (HCRU) endpoints will not be summarized or analyzed as described in the protocol or listed.

8.2.5. Summary of Efficacy Analyses

Table 2. Tabular Summary of Efficacy Analyses

Endpoint	Analysis Set	Statistical Method	Covariates/ Strata	Objective
Time to major cardiovascular event	FAS	Log rank test	Geographic region, complete statin intolerance	Primary analysis
		Cox proportional hazards regression	Treatment group/ geographic region, complete statin intolerance*	Decision on primary objective
		Plot of Kaplan-Meier Estimates		Support of primary objective
		Arjas plot	Geographic region × complete statin intolerance	
Time to premature discontinuation from the study	FAS	Log rank test	Geographic region, complete statin intolerance	Impact of premature discontinuation from the study
		Cox proportional hazards regression	Treatment group/ geographic region, complete statin intolerance*	
Time to major cardiovascular event	FAS	Multiple imputations for Cox proportional hazards model	Cox model: Treatment group/geographic region, complete statin intolerance* Imputation model: Treatment group set equal to placebo for all subjects, age, gender, BMI, geographic region, complete statin intolerance, baseline smoking status, baseline history of MI, baseline history of coronary revascularization, baseline history of coronary heart disease, baseline history of diabetes, baseline history of heFH/LDL-C \geq 190 ml/dL, baseline history of stroke, baseline history of congestive heart failure baseline history of chronic kidney disease.	Impact of informative censoring under the switch-to-control assumption

Endpoint	Analysis Set	Statistical Method	Covariates/ Strata	Objective
Time to CV death, non-fatal MI or non-fatal stroke	FAS	Log rank test	geographic region, complete statin intolerance	First key secondary endpoint; tested only if the primary objective is met
		Cox proportional hazards regression	Treatment group/ geographic region, complete statin intolerance*	Decision on secondary objective
		Plot of Kaplan-Meier Estimates		Support of key secondary objective
		Arjas plot	Geographic region × complete statin intolerance	
Time to all-cause death, non-fatal MI, non-fatal stroke, or hospitalization for unstable angina needing urgent revascularization	FAS	Log rank test	Geographic region, complete statin intolerance	Second key secondary endpoint; tested only if the primary objective is met
		Cox proportional hazards regression	Treatment group/ geographic region, complete statin intolerance*	Decision on secondary objective
Time to all-cause death, non-fatal MI, or non-fatal stroke	FAS	Log rank test	Geographic region, complete statin intolerance	Third key secondary endpoint; tested only if the primary objective is met
		Cox proportional hazards regression	Treatment group/ geographic region, complete statin intolerance*	Decision on secondary objective
Time to hospitalization for unstable angina needing urgent revascularization	FAS	Log rank test	Geographic region, complete statin intolerance	Fourth key secondary endpoint; tested only if the primary objective is met
		Cox proportional hazards regression	Treatment group/ geographic region, complete statin intolerance*	Decision on secondary objective
Time to CV death, non-fatal MI, non-fatal stroke, or hospitalization for	FAS	Log rank test	Geographic region, complete statin intolerance	Other secondary endpoint

Endpoint	Analysis Set	Statistical Method	Covariates/ Strata	Objective
unstable angina				
		Cox proportional hazards regression	Treatment group/ geographic region, complete statin intolerance*	Other secondary objective
Time to CV death	FAS	Log rank test	Geographic region, complete statin intolerance	Other secondary endpoint
		Cox proportional hazards regression	Treatment group/ geographic region, complete statin intolerance*	Other secondary objective
Time to any MI (fatal and non-fatal)	FAS	Log rank test	Geographic region, complete statin intolerance	Other secondary endpoint
		Cox proportional hazards regression	Treatment group/ geographic region, complete statin intolerance*	Other secondary objective
Time to fatal MI	FAS	Log rank test	Geographic region, complete statin intolerance	Other secondary endpoint
		Cox proportional hazards regression	Treatment group/ geographic region, complete statin intolerance*	Other secondary objective
Time to non-fatal MI	FAS	Log rank test	Geographic region, complete statin intolerance	Other secondary endpoint
		Cox proportional hazards regression	Treatment group/ geographic region, complete statin intolerance*	Other secondary objective
Time to any stroke (fatal and non-fatal)	FAS	Log rank test	Geographic region, complete statin intolerance	Other secondary endpoint
		Cox proportional hazards regression	Treatment group/ geographic region, complete statin intolerance*	Other secondary objective
Time to any stroke (fatal and non-fatal) of any etiology	FAS	Log rank test	Geographic region, complete statin intolerance	Other secondary endpoint
		Cox proportional hazards regression	Treatment group/ geographic region, complete statin intolerance*	Other secondary objective

Endpoint	Analysis Set	Statistical Method	Covariates/ Strata	Objective
Time to fatal stroke	FAS	Log rank test	Geographic region, complete statin intolerance	Other secondary endpoint
		Cox proportional hazards regression	Treatment group/ geographic region, complete statin intolerance*	Other secondary objective
Time to non-fatal stroke	FAS	Log rank test	Geographic region, complete statin intolerance	Other secondary endpoint
		Cox proportional hazards regression	Treatment group/ geographic region, complete statin intolerance*	Other secondary objective
Time to hospitalization for unstable angina	FAS	Log rank test	Geographic region, complete statin intolerance	Other secondary endpoint
		Cox proportional hazards regression	Treatment group/ geographic region, complete statin intolerance*	Other secondary objective
Time to hospitalization for congestive heart failure	FAS	Log rank test	Geographic region, complete statin intolerance	Other secondary endpoint
		Cox proportional hazards regression	Treatment group/ geographic region, complete statin intolerance*	Other secondary objective
Time to any coronary revascularization procedure	FAS	Log rank test	Geographic region, complete statin intolerance	Other secondary endpoint
		Cox proportional hazards regression	Treatment group/ geographic region, complete statin intolerance*	Other secondary objective
Time to CABG	FAS	Log rank test	Geographic region, complete statin intolerance	Other secondary endpoint
		Cox proportional hazards regression	Treatment group/ geographic region, complete statin intolerance*	Other secondary objective
Time to PCI	FAS	Log rank test	Geographic region, complete statin intolerance	Other secondary endpoint
		Cox proportional hazards regression	Treatment group/ geographic region, complete statin intolerance*	Other secondary objective

Endpoint	Analysis Set	Statistical Method	Covariates/ Strata	Objective
Time to any arterial revascularization	FAS	Log rank test	Geographic region, complete statin intolerance	Other secondary endpoint
		Cox proportional hazards regression	Treatment group/ geographic region, complete statin intolerance*	Other secondary objective
Time to all-cause death	FAS	Log rank test	Geographic region, complete statin intolerance	Other secondary endpoint
		Cox proportional hazards regression	Treatment group/ geographic region, complete statin intolerance*	Other secondary objective
		Plot of Kaplan-Meier Estimates		Support of other secondary objective
Reasons for all-cause death	FAS		Event rates and 95% CIs	
LDL-C: percent change from baseline to each post-randomization visit	FAS	MMRM	Treatment group, scheduled visit (categorical), baseline value (continuous), treatment × scheduled visit interaction, baseline value × scheduled visit interaction, geographic region, complete statin intolerance	Other secondary endpoint
		Plot of LS-Mean percent changes from baseline and 95% CI		
LDL-C: nominal change from baseline to each post-randomization visit	FAS	MMRM	Treatment group, scheduled visit (categorical), baseline value (continuous), treatment × scheduled visit interaction, baseline value × scheduled visit interaction, geographic region, complete statin intolerance	Other secondary objective
LDL-C: percent change from baseline to last post-baseline measurement	FAS	ANCOVA	Treatment group, baseline value, geographic region, complete statin intolerance	Supportive of other secondary objective

Endpoint	Analysis Set	Statistical Method	Covariates/ Strata	Objective
Total cholesterol: percent change from baseline to each post-randomization visit	FAS	MMRM	Treatment group, scheduled visit (categorical), baseline value (continuous), treatment × scheduled visit interaction, baseline value × scheduled visit interaction, geographic region, complete statin intolerance	Other secondary endpoint
		Plot of LS-Mean percent changes from baseline and 95% CI		
HDL-C: percent change from baseline to each post-randomization visit	FAS	MMRM	Treatment group, scheduled visit (categorical), baseline value (continuous), treatment × scheduled visit interaction, baseline value × scheduled visit interaction, geographic region, complete statin intolerance	
Triglycerides: nominal change from baseline to each post-randomization visit for log-transformed value	FAS	MMRM	Treatment group, scheduled visit (categorical), baseline value (continuous), treatment × scheduled visit interaction, baseline value × scheduled visit interaction, geographic region, complete statin intolerance	Other secondary objective
Non-HDL-C: percent change from baseline to each post-randomization visit	FAS	MMRM	Treatment group, scheduled visit (categorical), baseline value (continuous), treatment × scheduled visit interaction, baseline value × scheduled visit interaction, geographic region, complete statin intolerance	Other secondary endpoint
		Plot of LS-Mean percent changes from baseline and 95% CI		

Endpoint	Analysis Set	Statistical Method	Covariates/ Strata	Objective
VLDL-C: percent change from baseline to each post-randomization visit	FAS	MMRM	Treatment group, scheduled visit (categorical), baseline value (continuous), treatment × scheduled visit interaction, baseline value × scheduled visit interaction, geographic region, complete statin intolerance	Other secondary endpoint
RLP-C: percent change from baseline to each post-randomization visit	FAS	MMRM	Treatment group, scheduled visit (categorical), baseline value (continuous), treatment × scheduled visit interaction, baseline value × scheduled visit interaction, geographic region, complete statin intolerance	Other secondary endpoint
Apo-A-I: percent change from baseline to each post-randomization visit	FAS	MMRM	Treatment group, scheduled visit (categorical), baseline value (continuous), treatment × scheduled visit interaction, baseline value × scheduled visit interaction, geographic region, complete statin intolerance	Other secondary endpoint
Apo-B: percent change from baseline to each post-randomization visit	FAS	MMRM	Treatment group, scheduled visit (categorical), baseline value (continuous), treatment × scheduled visit interaction, baseline value × scheduled visit interaction, geographic region, complete statin intolerance	Other secondary endpoint
		Plot of LS-Mean percent changes from baseline and 95% CI		
Lp(a): nominal change	FAS	MMRM	Treatment group, scheduled visit	Other secondary objective

Endpoint	Analysis Set	Statistical Method	Covariates/ Strata	Objective
from baseline to each post-randomization visit in log-transformed value			(categorical), baseline value (continuous), treatment × scheduled visit interaction, baseline value × scheduled visit interaction, geographic region, complete statin intolerance	
hs-CRP: nominal change from baseline to each post-randomization visit for log-transformed value	FAS	MMRM	Treatment group, scheduled visit (categorical), baseline value (continuous), treatment × scheduled visit interaction, baseline value × scheduled visit interaction, geographic region, complete statin intolerance	Other secondary objective

* If model fitting of the Cox proportional hazards regression model fails to converge, complete statin intolerance will be removed as a stratification factor.
 
FAS = Full Analysis Set SAS = Safety Analysis Set MMRM = Mixed Model Repeated Measures CI = confidence interval ANCOVA = analysis of covariance
				

